 - Dilator Insertion: Immediately following dilator insertion
 - Post-Procedure Pain: 10-15 minutes following procedure
 - Overall Pain: Assessed after procedure
- Incidence of complications
- Provider reported ease of insertion

- Global satisfaction (acceptability) of procedure

Study Drugs

Experimental Group:

Xylocaine (lidocaine HCl) is a common local anesthetic that works by stabilizing the neuronal membrane by inhibiting the ionic fluxes required for the initiation and conduction of impulses. Local anesthetics of the amide type are thought to act within the sodium channels of the nerve membrane. According to the packaging insert, anesthesia is achieved within 5 minutes, depending on the area of application, and duration of anesthesia is approximately 20-30 minutes. It is used prior to many genitourinary procedures involving mucous membranes including the urethra, anus, and vulva. While no recommended dose is known for vaginal use prior to surgical abortion, recommended doses are known for the following procedures: 20 ml for proctoscopy/anoscopy; 10 ml for female urethral anesthesia as in cystoscopy. A single maximum dosage for 2% Xylocaine jelly is not established [Blanco 1982], however Lexicomp drug information for topical lidocaine jelly cites a maximum dose of 600 mg in any 12-hour period.

The serum toxicity of intracervical lidocaine is thought to be around 5 ug/ml [Blanco 1982] and a study looking at serum lidocaine levels 10 minutes after paracervical injection of 20 ml of 1% lidocaine (200 mg total) found mean blood levels of 0.9 to 1.61 ug/ml [McKenzie 1978].

Similarly, a study investigating vaginal anesthesia with 4ml of 10% lidocaine spray (400mg total) 5 minutes prior to high dose intracavitary brachytherapy found a significant decrease in procedural pain [Chen 1998]. This study also looked at serum lidocaine levels at various time points following administration and found that the 400mg dose never reached toxic levels in participants. These data are further supported by non-toxic levels seen after nasopharyngeal and oropharyngeal application in the studies cited above.

Based on this information, participants in the lidocaine gel group will self-administer 20 ml of 2% lidocaine HCl vaginally (400 mg total) 20-30 minutes prior to the start of the procedure. We are allowing a window of time to account for real life clinic practice and possible delays.

The product:

- XYLOCAINE® JELLY 2% (lidocaine hydrochloride) AstraZeneca

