- Known allergy to study medication (lidocaine)
- Any women not meeting inclusion criteria above will be excluded from participation

Study Procedures

This study will take place during subjects' cervical preparation visit. Following informed consent, participants will be randomized to a study group—group allocation information will be kept in a sealed, opaque envelope. Upon consenting for the study, a research coordinator will assign a unique subject ID number to the participant. This subject ID number's envelope will be opened to determine allocation. Participants, research staff, and health care provider will not be blinded to the allocation.

If the subject is randomized to the experimental group (self-administered lidocaine gel), she will be instructed on how to self-administer the gel vaginally by the study coordinator. She will insert 20ml of 2% lidocaine gel into her vagina using a pre-loaded syringe. After 15 minutes, the procedure will be begin.

If the subject is randomized to the control group (provider-administered paracervical block), cervical anesthesia and preparation will commence to standard.

For both groups, the research coordinator will collect demographic and medical history and document procedure data. For VAS scores, the research coordinator will administer the 100mm VAS on an iPad. Pain scores will taken "in real time". There is no follow-up for this study.

Data Collection

Data collection will be obtained through a REDCap survey.

Data to be collected include:

- Demographics
 - Location of procedure
 - MRN
 - Date enrolled
 - First name
 - Last name
 - Date of birth
 - Age
 - Phone number
 - Race
 - Ethnicity
- Medical History (Physical Exam and Ob/Gyn History)
 - Height
 - Weight

- BMI
- Gestational age
- Medication allergies
- Current medications
- Number of previous pregnancies
 - Number of previous vaginal deliveries
 - Number of previous cesarean sections
 - Number of previous abortions
 - Number of previous abortions after 16 weeks gestation
 - Number of miscarriages
- Medical problems
- Previous surgeries
 - Previous cervical surgeries
- Procedure Data
 - Provider type (i.e. resident, fellow, attending)
 - Provider reported ease of procedure
 - Uterine position
 - Initial cervical dilation
 - Number of osmotic dilators or laminaria placed
 - Time with lidocaine gel before tenaculum
 - Time with paracervical block before tenaculum
 - Total speculum time
 - Complications
- Procedure VAS Data
 - Anticipated
 - Baseline

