 - Speculum insertion
 - Paracervical block (control group only)
 - Tenaculum placement
 - Laminaria/osmotic dilator insertion
 - Post-procedure
 - Overall pain
- Acceptability Data
 - Gel leakage acceptability (experimental group only)
 - Likelihood to recommend procedure
 - Comfort with tampons
 - Maximum time willing to wait for pain control

Data Analysis and Monitoring

Enrollment will be reviewed bi-weekly by the research team. Given that there are minimal safety risks involved in this study, we do not plan to convene an independent Data Safety Monitoring Board (DSMB).

Data Management and Storage

Data will be entered into and stored on REDCap.

Methods of Analysis

Data will be exported from REDCap to SPSS Version 23.0 for analysis.

Perioperative characteristics will be examined among the groups using chi square test and fisher's exact test, where appropriate; mean and median VAS pain scores will be analyzed with Student's *t*-tests and non-parametric tests, respectively; mean and median overall satisfaction with pain control and provider reported ease of procedure via VAS scores will be compared using Student's *t*-tests and non-parametric tests, respectively; linear regression will be completed in multivariable analysis to identify predictors of pain.

Analysis and Dissemination of Results

Analysis will occur upon completion of study enrollment. The co-investigators plan to prepare at least one manuscript for submission to a peer-reviewed journal. In addition, the co-investigators will present the results of the study at conferences and meetings where appropriate.

Risks and Benefits

Participants are not promised any benefits from participating in the study.

Potential risks associated with this study are minimal. The risk to the participants' physical, psychological, economic, or social well-being in this study is not anticipated to be any different or greater from women not participating in the study.

The risks, side effects, and discomforts of the study, whether the subject receives lidocaine gel or lidocaine paracervical block, are expected to be similar and include:

- Side effects with medications
 - Lidocaine - with numbing medicine in a woman's cervix, there is an infrequent risk of getting a unusual taste in the woman's mouth, ringing in her ears, nausea or light-headedness. Rarely, a person can have a seizure from the numbing medicine.

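### Does the planned satisfaction comparison lack a variable, and the satisfaction objective a measure?

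*Combined protocol and SAP*

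**What the plan says.** Three places in the protocol bear on this outcome.

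- **Secondary Objectives.** The last two entries are the provider's rating of how easy insertion was and "Global satisfaction (acceptability) of procedure". Neither has a scale or a time point.
- **Data Collection.** The list opens with "Data to be collected include". Under Procedure Data it has "Provider reported ease of procedure". The Procedure VAS block holds pain scores only. A separate block headed "Acceptability Data" has four items: acceptability of gel leakage (gel arm only), "Likelihood to recommend procedure", comfort with tampons, and the longest acceptable wait for pain control.
- **Methods of Analysis.** Here "mean and median overall satisfaction with pain control and provider reported ease of procedure via VAS scores will be compared", means by Student's t-test and medians by non-parametric tests. None of the four acceptability items is mentioned.

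Study Procedures adds that the coordinator administers the 100 mm VAS on an iPad, and that "There is no follow-up for this study".

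**The concern.** The chain from objective to data item to test looks broken at two points.

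1. The analysis names satisfaction with pain control, and no listed item carries that name. If the form were built strictly from the list, the comparison would have nothing to run on. All data come from a single visit, so a question not asked then could not be recovered.
2. The objective concerns satisfaction with the procedure, while the analysis concerns satisfaction with pain control. The two can diverge: a woman may rate her pain relief well and still dislike inserting the gel, its leakage or the wait.

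The trial is open-label and is analysed once enrolment is complete. A measure left undesignated could therefore be picked after the results are known. Acceptability also matters to the interpretation: if the gel is no worse for pain, acceptability helps decide whether it is worth using.

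**Working it through.** **Counting the list.** The items under Data Collection are:

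| Block | Items | Satisfaction ratings |
|---|---|---|
| Demographics | 10 | 0 |
| Medical History | 15 | 0 |
| Procedure Data | 9 | 0 |
| Procedure VAS Data | 8 | 0 |
| Acceptability Data | 4 | 0 |
| Total | 46 | 0 |

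The check is 10 + 15 + 9 + 8 + 4 = 46. Only the last two blocks could reasonably hold a patient rating, so the more relevant count is 0 of 8 + 4 = 12. The literal observation is correct.

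**Is the list meant to be complete?** Its opening verb does not claim so, and its content shows that it is not. Study Procedures assigns every participant a subject ID and an allocated arm, and neither is on the list. No between-arm comparison could be made without the arm, so the arm must be recorded. Absence from this list is therefore weak evidence that an item is not collected.

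**Where do scales come from in this protocol?** Provider-reported ease is a useful comparator. It is listed under Procedure Data, outside the VAS block and with no scale. Only Methods of Analysis says that it is a VAS. The same sentence gives satisfaction its scale and its tests. The analysis section is thus a source of measurement detail for both outcomes, and a team following it would put a satisfaction VAS on the form.

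**Do the labels describe different outcomes?** Set side by side:

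| Secondary objective | Analysis sentence |
|---|---|
| Provider's ease of insertion | Provider's ease of procedure, VAS |
| Global satisfaction (acceptability) with procedure | Overall satisfaction with pain control, VAS |

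The two objectives stand next to each other, and one clause of the analysis covers two measures of the same kind. The ease label also shifts, from insertion to procedure, and nobody would read that as two endpoints. The plain reading is that the clause analyses these two objectives under loose wording.

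**Is the objective otherwise unmeasured?** No. It equates satisfaction with acceptability. Of the four acceptability items, one is confined to the gel arm, which leaves 4 − 1 = 3 open to both arms. One of these, "Likelihood to recommend procedure", speaks directly to global acceptability.

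**Does the point reach the primary result?** The stated sample size uses SD 22 mm, margin 15 mm, one-sided alpha 0.025 and power 80%. Assuming 1:1 allocation:

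n per arm = 2 × (1.960 + 0.842)² × 22² / 15² = 2 × 7.85 × 484 / 225 ≈ 33.8, rounded up to 34, so 68 in total.

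This matches the protocol. The recruitment target of 72 adds 4 women, or 4/72 = 5.6%. Satisfaction does not enter any of these figures.

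**The case for a change.** The best argument for a change is that the remedy costs almost nothing (at most one iPad question for 72 women, or wording alone if the item already exists) while an omission could not be repaired after the visit. Satisfaction with pain control is also narrower than satisfaction with the procedure. No acceptability item is designated as the measure of the objective, none has a stated response scale, and none is given a test. The clause on chi-square and Fisher's tests covers perioperative characteristics, not acceptability.

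Part of this stands. The terms do differ between sections, the time point of the satisfaction rating is not written down, and the acceptability items have no named analysis. The irrecoverable loss, however, requires a team to build the form from an openly partial list while ignoring its own analysis section, and nothing in the documents suggests that. Selective choice is limited too, because the protocol names one satisfaction outcome with its scale and tests. A between-arm result drawn from the other acceptability items would be read as descriptive. Carrying both pain-control satisfaction and global satisfaction as separately tested endpoints would add a second test that the protocol does not call for.

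**Conclusion.** No change to the plan is needed. The mismatch in wording is real, but it is missing detail on one secondary outcome. No stated rule or number gives a wrong result. Methods of Analysis already requires a satisfaction VAS compared between arms, and the single-visit design leaves the end of that visit as the only sensible time to ask for an overall rating. The acceptability items can be summarised by arm where both arms answer them.

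In size, one of the two measures in the analysis sentence is missing from a list that is visibly incomplete. The primary comparison, margin and sample size are untouched.

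The conclusion rests on two assumptions: that the team followed its own analysis section when building the REDCap form, which the documents do not show, and that the satisfaction clause is the analysis of the satisfaction objective, which is the natural reading but is not stated. If the form turned out to have no such item, the loss would be that one secondary comparison, with likelihood to recommend still available as a related measure.
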